## 1 INTRODUCTION

This document describes the statistical procedures that will be utilized for the study of Comparative Immunogenicity of Concomitant vs Sequential mRNA COVID-19 and Influenza Vaccinations. This statistical analysis plan (SAP) describes the methods of statistical analysis. In this study, participants will be randomly assigned to receive an approved quadrivalent cell culture-based influenza vaccine (cclIV4) and mRNA COVID-19 vaccine (Moderna) either concomitantly or sequentially, 28 days apart. Participants (aged 6-11 years and 18-64 years) will be enrolled in the 2023-2024 influenza season. Enrolled participants will be randomized to one of the following interventions (2:1:1) using a permuted block method stratified by age group (aged 6-11 years and 18-64 years) and site: (1) concomitant administration of the mRNA COVID-19 vaccine (Moderna) and quadrivalent influenza vaccine (cclIV4); (2) sequential administration of the quadrivalent influenza vaccine (cclIV4) at Visit 1 (day 0) and the mRNA COVID-19 vaccine (Moderna) at Visit 2 (day 28); (3) sequential administration of the mRNA COVID-19 vaccine (Moderna) at Visit 1 (day 0) followed by the quadrivalent influenza vaccine (cclIV4) at Visit 2 (day 28).

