### 2.2 Exploratory

EO1: To determine baseline and post-vaccination influenza antibody titers by microneutralization (MN), in a subset of samples, against cclIV4 vaccine antigens following concomitant administration with mRNA vaccine or alone.

EO2: To determine baseline and post-vaccination SARS-CoV-2 antibody binding titers and ACE2 binding inhibition and viral neutralization, on a subset of specimens, against Moderna mRNA COVID-19 vaccine antigens following concomitant administration with cclIV4 or alone.

EO3: To determine duration and rate of waning of influenza HAI and MN antibody titers against cclIV4 vaccine antigens and circulating influenza viruses.

EO4: To determine duration of and rate of waning of SARS-CoV-2 antibody titers and viral neutralization titers, on a subset of samples, against Moderna mRNA COVID-19 vaccine antigens and circulating SARS-CoV-2 variants.

EO5: To determine influenza HAI and MN antibody titers against circulating influenza viruses during baseline and post-vaccination or post-infection.

EO6: To determine SARS-CoV-2 antibody binding titers and viral neutralization titers (in a subset of samples) against circulating SARS-CoV-2 variants during baseline and post-vaccination.

EO7: To compare the frequencies of antigen-specific T and B cells utilizing conventional ELISPOT assays, high-dimensional flow cytometric analysis of innate and adaptive immune cell

phenotype characterization using fluorochrome-conjugated antigen tags, and intracellular cytokine staining to 2023-24 cclIV4 and mRNA COVID-19 vaccines administered either concomitantly or sequentially, 28 days apart.

EO8: To compare transcriptome, B cell receptor (BCR) and T cell receptor (TCR) diversity of antigen-specific cells and assess serological antibody repertoire (clonotypes) using 10X genomics platform, and liquid chromatography/mass spectroscopy in a subset of participants.

EO9: To investigate the waning of antigen-specific B cells and antibody clonotypes in a subset of participants.

EO10: To describe safety of concomitant versus sequential administration of cclIV4 and mRNA COVID-19 vaccination.

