#### 3.2 Exploratory

EO1:

- I. Proportion of participants in each vaccination group with a seroprotective MN (in a subset of samples) titer ( $\geq 1:40$ ) pre- and post-cclIV4 immunization for each 2023-24 influenza vaccine antigen
- II. Proportion of participants in each vaccination group achieving MN (in a subset of samples) seroconversion (a titer  $\geq 1:40$  following cclIV4 if the baseline titer is  $< 1:10$  or a four-fold rise in titer if the baseline titer is  $> 1:10$ ) following cclIV4 vaccination for each 2023-24 influenza vaccine antigen
- III. HAI (in a subset of samples) MN for each 2023-24 influenza vaccine antigen pre- and post-cclIV4 in each vaccination group
- IV. GMFR in MN (in a subset of samples) titers for each 2023-24 influenza vaccine antigen in each vaccination group

EO2. GMT for SARS-CoV-2 binding antibody titer and viral neutralization titer (for a subset of samples) pre- and post-vaccination with mRNA COVID-19 vaccine

EO3:

- I. HAI and MN GMT for each 2023-24 influenza vaccine and circulating influenza virus antigens at visit 1, visit 2, visit 3, and visit 4 for each vaccination group
- II. Geometric mean fold change in HAI and MN titers for each vaccination group from visit 1 to visit 2, visit 3, and visit 4 for each 2023-24 influenza vaccine and circulating influenza virus antigen

EO4:

- I. SARS-CoV-2 binding antibody and viral neutralization GMT for each mRNA COVID-19 vaccine and circulating SARS-CoV-2 virus antigens at visit 1, visit 2, visit 3, and visit 4 for each vaccination group
- II. Geometric mean fold change in SARS-CoV-2 and viral neutralization (in a subset of samples) titers for each vaccination group from visit 1 to visit 2, visit 3, and visit 4 for each COVID-19 Moderna mRNA COVID-19 vaccine and circulating SARS-CoV-2 virus antigen

EO5

- I. Proportion of participants in each vaccination group with a seroprotective titer ( $\geq 1:40$ ) pre- and post-cclIV4 immunization (visits 1-3) and/or pre- and post-influenza infection (acute and convalescent visits), if applicable, for each 2023-24 circulating influenza virus antigen

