### *Serology*

Microneutralization (MN), SARS-CoV-2 binding antibody and viral neutralization, and circulating virus objectives will all use the same statistical methods as the primary HAI objective. Waning objectives will use parametric models to estimate the rate of antibody decline by time since vaccination. Estimated GMTs and fold change will be presented for each time point with their associated 95% confidence intervals.

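### Duration results are tabulated by visit, so for the vaccine given at Visit 2 the arms are compared about 28 to 42 days apart in time since that vaccine

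*SAP*

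**What the plan says.** The influenza waning objective (SAP 2.2, EO3) is "To determine duration and rate of waning of influenza HAI and MN antibody titers against cclIV4 vaccine antigens and circulating influenza viruses"; EO4 is its SARS-CoV-2 counterpart. In SAP 3.2 the first endpoint under both EO3 and EO4 is a set of GMTs "at visit 1, visit 2, visit 3, and visit 4 for each vaccination group". The second is a fold change from baseline; for influenza it reads "Geometric mean fold change in HAI and MN titers for each vaccination group from visit 1 to visit 2, visit 3, and visit 4".

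SAP 9.2 (Serology) gives the analysis in two sentences. The first sets the time scale for the rate: "Waning objectives will use parametric models to estimate the rate of antibody decline by time since vaccination". The second sets the reporting: "Estimated GMTs and fold change will be presented for each time point with their associated 95% confidence intervals". The SAP does not define duration, name the curve form, say which arms are contrasted for waning, or say how by-visit results will be aligned across arms.

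Protocol Table 1 (5.4.1) counts Visit 2 from Visit 1, and counts Visits 3 and 4 from Visit 2. Group i receives both vaccines at Visit 1. Group ii receives influenza vaccine at Visit 1 and COVID-19 vaccine at Visit 2; group iii the reverse.

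**The concern.** A by-visit table compares like with like only if the same visit means the same time since the vaccine whose antibody is measured. That is true for a vaccine given at Visit 1. It is not true for one given at Visit 2: at Visits 3 and 4 the later-dosed arm has had less time to decline. Schedules with identical responses and identical decay would then show different GMTs, always with the later-dosed arm higher. The fold change from Visit 1 shifts by the same factor, since its denominator is a pre-vaccination titre in every arm.

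Duration of response under the two schedules is part of the protocol's title. Taken literally, the stated endpoints could credit sequential vaccination with better persistence when only the calendar differs.

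**Working it through.** **Inputs from Protocol 5.4.1.** Visit 2 is on day 28 (window 28 to 42). Visit 3 is 28 days after Visit 2 (28 to 92). Visit 4 is 152 days after Visit 2 (± 30).

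**Reproducing the plan's visit days.** 28 + 28 = 56 and 28 + 152 = 180, matching the stated study days. (The Visit 3 text gives days 56 to 120, while Table 1 allows up to 42 + 92 = 134. These should be reconciled, but the offset below does not depend on them.)

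**Target days since the vaccine measured.**

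| Antibody | Group | Visit 3 | Visit 4 |
|---|---|---|---|
| Influenza | i, ii | 56 | 180 |
| Influenza | iii | 28 | 152 |
| SARS-CoV-2 | i, iii | 56 | 180 |
| SARS-CoV-2 | ii | 28 | 152 |

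The offset equals the time from Visit 1 to Visit 2: 28 days on target and 42 at the late edge of the window (Visit 3: 70 v 28; Visit 4: 194 v 152). It can be shorter than 28 days, because Protocol 6.3 allows the second vaccine before Visit 2, and Protocol 5.4.3 allows vaccination outside the window.

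**Effect on the by-visit GMT.** Assume identical exponential decay in all arms. The ratio of later-dosed to earlier-dosed arm is 2^(gap / half-life), the same at Visits 3 and 4. The half-lives are assumptions.

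| Half-life (days) | 28-day gap | 42-day gap |
|---|---|---|
| 60 | 1.38 | 1.62 |
| 90 | 1.24 | 1.38 |
| 120 | 1.18 | 1.27 |
| 180 | 1.11 | 1.18 |
| 365 | 1.05 | 1.08 |

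If titre instead falls as days to the power −b, with b assumed between 0.3 and 1.0, the ratio for a 28-day gap is 2^b = 1.23 to 2.00 at Visit 3 and (180/152)^b = 1.05 to 1.18 at Visit 4.

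**Could this pass for a finding?** A simulation used 300 v 150 adults, identical exponential decay, Visit 2 spread over its window, and assumed log2 SDs of 1.3 between and 0.5 within participants. A two-sided 5% by-visit comparison at Visit 4 declared a difference in 99%, 79%, 55%, 29% and 10% of 2,000 runs at half-lives of 60, 90, 120, 180 and 365 days. On the time-since-vaccination scale the same data returned matching half-lives in both arms (60/60, 90/90, 120/120, 179/180, 365/366), and equal rates were rejected in 4.6 to 5.9% of runs.

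**Effect on the slope.** Under exponential decay a constant-rate slope does not depend on the sampling days, so the slope ratio is 1.0. Under the power law, least-squares slopes on days {28, 152} and {28, 56, 180} have ratio 1.198 for any b. Spreading visits evenly within 14 days after target gives about 1.21; spreading them over the full Table 1 windows gives 1.007. Putting every Visit 2 on day 42 would give 1.43, but that is the far corner of the window.

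**The case against.** The strongest reply is that the remedy is already half written: SAP 9.2 models the rate of decline by time since vaccination. That stands, and it settles the rate. It does not settle the by-visit GMTs and fold changes, which are the only endpoints SAP 3.2 lists under the waning objectives.

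A reader might go further and infer that the modelled rate is distorted too, so that the by-visit table would show the later-dosed vaccine as more durable while the slope showed it waning faster. The documents do not support this. The SAP says the models are parametric and nowhere says constant rate. The slope shifts only if a single constant rate is chosen and true decline is faster early, and then by an amount that depends on visit adherence. Nor can the largest values of the two effects occur together: the 1.62-fold GMT ratio assumes exponential decay, under which the slope effect is nil.

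It is also fair to say that these objectives are exploratory, that no between-arm waning contrast at Visit 3 or 4 is named, and that each arm's dosing day is stated, so a careful reader could see the offset. These points limit the weight of the concern. They do not remove it: SAP 9.2 applies two-sided 5% tests to all exploratory endpoints, and the endpoints are laid out for each group, which invites the comparison.

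**Conclusion.** The concern holds for the by-visit duration results of the vaccine given at Visit 2: influenza in group iii against groups i and ii, and SARS-CoV-2 in group ii against groups i and iii. With no true difference, the Visit 4 GMT in the later-dosed arm would be higher by about 5 to 38% for a 28-day gap and 8 to 62% for a 42-day gap. These figures rest on identical exponential decay and assumed half-lives of 365 down to 60 days; for slow decay the effect is small.

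Influenza i v ii, the contrast used for the primary objective in SAP 9.1, and SARS-CoV-2 i v iii are aligned and not affected. The rate of decline is not distorted by the offset itself. A slope shift of roughly 0 to 20% under ordinary visit patterns remains possible, but only if a constant rate is fitted to a decline that is faster early.

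**What to change.** In SAP 9.2, for EO3 and EO4, carry the time-since-vaccination scale through to the reported duration results:

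- Index each sample by actual days since the vaccine whose antibody is measured.
- State one curve form, used in all arms, that can allow faster early decline.
- From that model report each arm's GMT at common days since that vaccine, for example day 28 and day 150, with the fold change between them and 95% confidence intervals. Base duration comparisons between schedules on these.
- Keep the by-visit tables as description, with median days since each vaccine shown by arm.

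The cost is SAP wording and slightly more analysis. The model is already planned, the calculation needs only vaccination and blood-draw dates, and no visit or sample is added. The downside is some reliance on the model between sampling days: on target, day 150 is close to a sample in the later-dosed arm (152) but lies between samples in the others (56 and 180).

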### *Cell Mediated Immunity*

Assay results will be presented by time point and treatment group. Summary statistics (e.g., mean, standard deviation, median) will be presented for continuous outcomes. Categorical variables will be described with frequencies and percentages. Continuous outcomes will be log transformed as appropriate for each assay.

### *Safety*

Safety endpoints will be assessed using the mITT population.

Frequency and proportion of participants reporting injection site and/or systemic reactions during the first 3 days following each vaccination visit will be stratified by severity and their impact on health, and reported along with the difference in proportions reporting moderate/severe symptoms between groups and a 95% confidence interval for the difference.

Frequency and proportion of participants reporting a change in health status requiring hospital admission (including a description of the event) during the study period will be reported along with the difference in proportions between groups and a 95% confidence interval for the difference.

## 10 DERIVED AND TRANSFORMED DATA

Values below the limit of detection will be set to half the limit.

HAI and MN titers will log 2 transformed for calculation of GMT and GMFR.

**Fold Rise or Fold Change** is defined as a numeric variable for participants with non-missing values as:

post vaccination titer/pre vaccination titer

**Geometric Mean Titer (GMT)** is calculated by taking the anti-log of the mean of the log transformed titers

**Geometric Mean Fold Rise/Change (GMFR)** is calculated by taking the anti-log of the mean of the log transformed fold rise.

**Seroconversion** is defined as binary variable for participants with non-missing values as:

= 1, if achieving a HI antibody titer  $\geq 1:40$  following influenza vaccination if the baseline titer is  $< 1:10$  or a four-fold rise in titer if the baseline titer is  $> 1:10$

= 0, otherwise

**Seroprotection** is defined as binary variable for participants with non-missing values as:

= 1, if achieving a HI antibody titer  $\geq 1:40$

= 0, otherwise

## **APPENDIX 1**

### **Protocol Violations for Exclusions from Immunogenicity Analysis**

1. Missed visit/visit not conducted
2. Visit occurred outside of acceptable window
3. No pre- and/or post-vaccination blood draw or insufficient volume for assay analysis for respective vaccine
4. Did not meet inclusion
5. Met exclusion criteria
6. Delayed vaccine administration
7. Missed vaccine administration
8. Study product temperature excursion

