8 STATISTICAL ANALYSIS

8.1 Study Populations

There will be two study populations: the modified Intent-to-Treat (mITT) and Immunogenicity populations. The mITT population will include any participant who was enrolled, randomized, and received at least one vaccine. The Immunogenicity Population is a subset of the mITT Population that includes only subjects who received at least one vaccine, provide visit 1 and visit 2 blood draws available for analysis within the protocol-defined time frame, and with no protocol violations affecting immunogenicity. These protocol violations will be listed in the Statistical Analysis Plan. Statistical analyses of safety outcomes will be performed for the mITT population, and immunogenic outcomes will be analyzed for the Immunogenicity Population.

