## 6.3 Influenza Immunogenicity Population

The Influenza Immunogenicity Population is a subset of the mITT Population that includes only subjects who received both vaccines, provide visit 1 and visit 2 blood draws available with HAI titer results for analysis within the protocol-defined time frame, did not have an influenza or SARS-CoV-2 infection between visits 1 and 2, and had no protocol violations affecting immunogenicity. Protocol violations affecting the immunogenicity analyses are defined in the Statistical Analysis Plan (SAP) Appendix 1. The acceptable visit window for sample analysis will be +14 days from the target date. Should 10% or more of the total study population be excluded from the Influenza Immunogenicity Population due to missing the visit window, then an additional analysis will be performed including these subjects with the missing visit window exclusion.

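### The SAP's exclusion list is not tied to the visits or doses an analysis uses, so events after the Visit 2 blood draw can remove participants from the primary HAI comparison

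*SAP*

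**What the plan says.** SAP 6.3 builds the Influenza Immunogenicity Population from conditions that must all be met. Participants must have had both vaccines and must "provide visit 1 and visit 2 blood draws available with HAI titer results for analysis within the protocol-defined time frame". They must have had no influenza or SARS-CoV-2 infection between those two visits, and must have "had no protocol violations affecting immunogenicity". The section then states: "Protocol violations affecting the immunogenicity analyses are defined in the Statistical Analysis Plan (SAP) Appendix 1". SAP 6.2 also requires both vaccines for the mITT population, of which this population is a subset.

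Appendix 1 lists eight violations. Item 1 is "Missed visit/visit not conducted" and item 2 is "Visit occurred outside of acceptable window"; neither names a visit. Item 3 is tied to a vaccine: "No pre- and/or post-vaccination blood draw or insufficient volume for assay analysis for respective vaccine". Items 6 and 7 cover delayed and missed vaccine administration, without saying which dose or visit. On timing, 6.3 says "The acceptable visit window for sample analysis will be +14 days from the target date", again without a visit number.

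Protocol 8.1 is looser on vaccination. Its mITT and Immunogenicity populations need at least one vaccine, and participants in the latter must "provide visit 1 and visit 2 blood draws available for analysis within the protocol-defined time frame, and with no protocol violations affecting immunogenicity".

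SAP 9.1 compares groups i and ii before and 28 to 42 days after influenza vaccination. SAP 9.2 uses the immunogenicity population for all serology and cell-mediated objectives, including waning, which draws on Visits 3 and 4.

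**The concern.** Groups i and ii both receive the influenza vaccine at Visit 1, so the primary endpoint is complete once the Visit 2 blood is drawn. An exclusion triggered after that point discards valid primary data and makes entry to the analysis depend on something that happened after the outcome was measured. Where only one arm can trigger the exclusion, the randomised comparison is no longer protected against selection.

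Because one participant-level population serves analyses that span all four visits, and no rule says exclusion works visit by visit, a programmer would have to decide what items 1 and 2 cover. In an open-label trial, that decision belongs in the SAP, before analysis.

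**Working it through.** The plan gives no power, effect size, standard deviation, dropout rate or expected exclusion rate, so there is no stated figure to reproduce. The check compares the texts first and then illustrates the possible size.

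**1. Missed and late visits (items 1 and 2).** Set the SAP window of target plus 14 days against Protocol Table 1:

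| Visit | Protocol window | Target + 14 days |
|---|---|---|
| 2 | 28–42 days after Visit 1 | 28–42: agrees |
| 3 | 28–92 days after Visit 2 | 28–42: 92 − 42 = 50 permitted days fall outside |
| 4 | 152 ± 30 = 122–182 days after Visit 2 | 152–166: days 122–151 and 167–182 fall outside |

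The SAP rule fits only Visit 2. That suggests Visit 2 was meant. Applied to every visit, however, the rule would exclude people who attended Visit 3 or 4 inside the protocol window.

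**2. Missed and delayed doses (items 6 and 7).**
- Protocol 5.1: at Visit 2, blood is taken before vaccination. Group ii's post-influenza sample therefore precedes its COVID-19 dose.
- SAP 6.2, 6.3 and item 7: a group ii participant who gives that blood and does not then receive the COVID-19 dose is excluded. This needs no interpretation.
- Item 6: a delayed dose can have the same result. Protocol 5.3.3 foresees temporary delay at Visit 2.
- Group i receives both vaccines at Visit 1 and has no dose due after its primary sample.

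The people affected are those who attend Visit 2 and give blood but are not vaccinated, or are vaccinated late. Someone who misses Visit 2 altogether has no primary sample under any rule.

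**3. Illustrative size.** Randomising 800 at 2:1:1 gives 400, 200 and 200, so groups i and ii total 600. All loss rates below are assumptions.

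*Equal loss d from both groups* (literal reading of items 1 and 2). The standard error is multiplied by 1/√(1 − d). Power for an effect that had an assumed 80% power before loss is Φ((1.960 + 0.842)√(1 − d) − 1.960).

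| d | Lost of 600 | SE multiplier | Power |
|---|---|---|---|
| 5% | 30 | 1.026 | 78.0% |
| 10% | 60 | 1.054 | 75.7% |
| 20% | 120 | 1.118 | 70.7% |
| 30% | 180 | 1.195 | 65.0% |

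*Loss f from group ii only* (items 6 and 7). The SE multiplier is √[(1/400 + 1/(200(1 − f))) / (1/400 + 1/200)].
- f = 5% (10 people): √(0.007763/0.007500) = 1.017.
- f = 10% (20 people): √(0.008056/0.007500) = 1.036.

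If those excluded differ from those kept by δ log2 titre units, the GMT ratio moves by a factor of 2^(fδ). With f = 10%, this is 2^0.05 = 1.035 for δ = 0.5 and 2^0.10 = 1.072 for δ = 1. If those excluded have the same titre distribution as those kept, there is no shift.

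**The case against.** A reader might infer that the SAP drops a participant from the primary analysis for any missed or late visit. The documents do not say so. SAP 6.3 names only Visits 1 and 2 for blood and for intervening infection, and it limits violations to those affecting immunogenicity. A missed Visit 4 cannot alter titres already measured at Visits 1 and 2. The 14-day window fits only Visit 2. Items 1, 2, 3 and 7 can be read as restating the conditions of 6.3. The vaccine qualifier in item 3 may be there only because one list serves both the influenza and the SARS-CoV-2 populations. This stands: for items 1 and 2 the finding is an ambiguity, and the narrower reading is the likelier one.

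A reader might also infer that attendance at Visits 3 and 4 would differ by arm because group ii has to return for its second vaccine. That return is Visit 2 itself, which the primary analysis needs in any case. At Visits 3 and 4 both groups come only for blood draws, and nothing in the documents points to a difference between them.

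SAP 6.3 does offer some protection: an additional analysis if at least 10% of the total study population, 80 of 800, is excluded for missing the window. It does not cover missed visits or missed or delayed doses. The MCAR statement in SAP 7.2 concerns missing values and does not justify discarding observed ones.

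None of this answers the vaccine conditions, which are explicit for a missed dose and can operate after the endpoint in group ii only.

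**Conclusion.** The concern holds in two parts of different strength. Items 1 and 2 leave open which visits they cover. The literal reading would let a missed or late Visit 3 or 4 remove complete primary data, but the context favours Visits 1 and 2. Item 7, together with the both-vaccines requirement, definitely excludes group ii participants who miss a dose due after their primary sample, and item 6 can exclude those whose dose is delayed. Group i cannot be excluded in this way, and the both-vaccines rule departs from Protocol 8.1.

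The size cannot be derived from the documents. The loss rates, the 80% starting power and the titre differences used above are all assumptions. They indicate a modest loss of precision: about 5% on the standard error for a 10% loss from both groups, and less than 4% for a 10% loss from group ii alone. The main reason to act on the vaccine conditions is selection in one arm, whose direction and size are unknown.

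**What to change.** 1. **Primary group i versus ii HAI comparison.** State that only visit, window and vaccine deviations up to and including the Visit 2 blood draw lead to exclusion. Require receipt of the vaccine or vaccines assigned at Visit 1 instead of both vaccines.
2. **SAP 6.2 and 6.3.** Bring the vaccination requirement into line with Protocol 8.1. Without this, rewording item 7 restores nobody, because the both-vaccines condition would still exclude the same people.
3. **Other analyses.** Apply items 1 and 2 only to the visits an analysis uses: Visit 3 where it supplies the post-vaccination sample (group iii influenza, group ii COVID-19), and Visits 3 and 4 for waning. A missed or late Visit 3 or 4 should remove only that visit's result. SAP 6.4 relies on the same list and needs matching wording.
4. **Windows.** Reconcile the 14-day rule with the Table 1 windows for Visits 3 and 4, or state that it applies to Visit 2 only.

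The cost is a SAP amendment before analysis and evaluability flags per visit and endpoint in place of one participant-level flag. Changing 6.2 also widens the mITT population used for safety, which Protocol 8.1 already defines by at least one vaccine. No new data are needed.
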